Neuropathic pain is difficult to manage in PLWH. Studies of serotonin reuptake inhibitors, anti-epileptics, topical analgesics, HIV entry inhibitors, and anti-arrhythmics for the relief of neuropathic pain in PLWH show no efficacy.²⁸⁻³⁵ Subsequently, neuropathic pain is frequently managed with opioids, despite a high potential for misuse and use disorder.³⁶ PLWH are more likely to receive opioids for pain than those without HIV.³⁷⁻⁴¹ With the opioid epidemic and lack of evidence for chronic opioids for pain management, national guidelines for the treatment of pain in PLWH recommend medical cannabis and other non-opioid therapies.⁹ *PLWH are seeking medical cannabis, yet little evidence is available to guide clinical decision-making. Studies are needed to examine mechanisms, risks, and benefits of medical cannabis in PLWH.*

Medical cannabis legalization is rapidly expanding. Medical cannabis is legal in 37 states and recreational cannabis in 18 states.⁴² Acceptance of the therapeutic use of cannabis continues to grow, with increasing state and local legislative action.⁴³ Despite this, cannabis remains heavily restricted at the federal level. Federally, cannabis is classified as a Schedule 1 substance with “no currently accepted medical use and a high potential for abuse.”⁴⁴ This classification, which includes substances like heroin, has important research

[figure not shown]

Figure 1. Adapted Biopsychosocial framework for neuropathic pain in HIV and how it can be interrupted by THC and CBD

implications. Currently, only two entities can produce and supply cannabis to US researchers.⁴⁵ Cannabis products available for research are limited in scope and not comparable to products available in dispensaries.⁴⁶ Along with barriers to obtaining medical cannabis, *federal regulations require directly observed use of research cannabis products in settings such as human labs. Thus, clinical trials of medical cannabis for chronic pain with research cannabis provided by the federal government are infeasible.* Consequently, in the US, over the past 30 years, only two short term (5-12 days) RCTs in human labs have tested the effect of cannabis on neuropathic pain in PLWH.^{47,48}

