Medical cannabis policy in New York. In 2016, NY's Medical Marijuana Program (NYMMP) was implemented.⁴⁹ To be certified for medical cannabis, individuals must meet qualifying conditions, which include neuropathy, severe or chronic pain, and HIV. Medical cannabis products must be purchased from a state-licensed dispensary, which reports dispensed products, including milligrams of THC and CBD content and route of administration, to the NY Prescription Monitoring Program (PMP).⁴⁹ All products are oil extracts and are tested by the NY State Department of Health's lab to confirm content. *Because the precise THC/CBD content is reliable and known in NY's medical cannabis products, we have a unique opportunity to rigorously examine how medical cannabis affects neuropathic pain in PLWH.*

As of December 2020, over 3000 physicians and 130,000 patients are registered with the NYMMP.⁵⁰ Of patients, 75% have chronic or severe pain.⁴⁹ In the Montefiore Medical Cannabis Program (in which I am a provider), approximately 25% certified for medical cannabis are PLWH.

The mechanism of cannabis' analgesia in PLWH is complex. Cannabis acts at several different points of the BPS framework of neuropathic pain (Figure 1). THC and CBD act through two main receptors: CB1 and CB2. CB1 is primarily in the brain and spinal cord, and CB2 is mainly on macrophages and macrophage-derived cells that are part of the immune system and inflammatory response. Both THC and CBD act on these receptors but in different ways.⁵¹

THC achieves analgesic, anti-inflammatory, and muscle-relaxant effects through partial agonist action at CB1 and CB2.⁵² Psychoactive symptoms (anxiety, memory suppression) occur through THC's binding to CB1.⁵³ CBD weakly binds to CB1 and CB2, and has anti-inflammatory, anti-spasmodic, and analgesic effects in animal models.⁵³⁻⁵⁶ When CBD is used with THC, other receptors are activated to regulate pain perception.⁵³

CBD may reduce pain by reducing psychological symptoms. Neuropathic pain is associated with anxiety and depression.⁵⁷ Preclinical and clinical studies report reduced anxiety with CBD.⁵⁸⁻⁶¹ However, it is not known if anxiety improves or worsens when CBD is taken with THC. In cohort studies of street cannabis use, cannabis caused increased depression, but it is unknown how THC and CBD contribute to this.^{62,63}

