Unregulated cannabis, opioid, cocaine, or benzodiazepine use in the past 30 d	SQ, U

records, pharmacy records, and blood and urine samples (see Table 8). Our primary independent variable will be the initial soft-gel product obtained

from the medical cannabis dispensary, and our primary outcome will be self-reported pain severity using the Brief Pain Inventory severity subscale.

2.A. Settings: Montefiore Health System (Montefiore) is the largest healthcare system in the Bronx, NY with 11 hospitals and over 200 community clinics. Directed by [name] (Primary Mentor), the Montefiore Medical Cannabis Program includes 2500 patients certified by 25 physicians; approximately 25% of patients are PLWH. Vireo is a medical cannabis company with dispensaries in 11 states; two dispensaries are located in the NYC area. As of August 2020, in NY, Vireo served over 30,000 unique patients. Vireo staff will refer potential participants to the study and facilitate study retention; recruitment will occur at dispensaries.

2.C. Research visits and data collection.

Eligibility criteria. *Inclusion criteria* are: 1) ≥ 18 years old; 2) diagnosis of HIV 3) fluency in English; 4) actively certified for medical cannabis (medical records); 5) no medical cannabis dispensed in 60 days or used within the previous 30 days; 6) intent to have new soft-gel capsule product dispensed at Vireo (PMP or medical record); 7) ICD-10 diagnosis code for neuropathic pain, OR neuropathic pain in problem list of electronic medical record, OR neuropathic pain per medical cannabis certification form, OR Neuropathic Pain Questionnaire Short Form >0 .

Exclusion criteria are: 1) inability to provide informed consent; 2) inability to complete 14 weeks of study visit; 3) medical cannabis use within 30 days prior to enrollment; 4) unique pain symptoms (e.g. multiple sclerosis, rheumatoid arthritis); 5) terminal illness; 6) current or prior psychotic disorder; 7) unregulated cannabis, opioid, cocaine, or benzodiazepine use in the past 30 days (self-report and urine drug screen); 8) dispensed opioids or benzodiazepines within 60 days of enrollment; 9) non-steroidal anti-inflammatory (NSAID) use within 7 days prior to enrollment; 10) steroid use within the past 14 days with duration of therapy >21 days; 11) COVID vaccination within 14 days of screening.

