Aims 1-4	Medical cannabis use	Initial soft-gel capsule dispensed at Vireo Certification for medical cannabis (date, doctor, conditions) All medical cannabis products dispensed (date, product, dose, amount dispensed) Self-reported medical and unregulated cannabis use (product, # of days used, route, dollar amount of unregulated cannabis purchased, ASI)	PR MR PR TQ
Primary outcome variables			
Aims 1, 4	Pain Severity	Brief Pain Inventory (BPI) Severity subscale ⁹⁰	TQ
Secondary outcome variable			
Aims 2, 4	Inflammatory cytokines	Pro-inflammatory cytokines (TNF α , IL-6) Anti-inflammatory cytokines (IL-4, IL-10)	B B
Aims 3, 4	Adverse events	VL, CD4 count AIDS Clinical Trial Group (ACTG Adherence) ⁹³ , Visual Analog Scale (VAS) ⁹⁴ ARVs dispensed Depression (Center for Epidemiological Studies-Depression Scale [CES-D])), Generalized Anxiety Disorder (GAD-7) ⁹⁶	B IQ PR IQ
Other measures			
Aims 1-4	Sociodemographics	Age, race/ethnicity, education, insurance, sex, gender	IQ
Aims 1-4	Pain characteristics	Brief Pain Inventory (BPI) Interference subscale ⁹⁰ Pain catastrophizing scale ⁹⁸ , Pain DETECT questionnaire ⁸⁴	IQ IQ
Aims 1-4	Pain treatment	Pain treatment (SSRIs, gabapentin, injections, physical therapy)	IQ/MR/PR
Aim 3	Substance use/disorder	Smoking (Fagerstrom test for nicotine dependence) ⁹⁹ , Alcohol Use Disorders Identification Test (AUDIT) ¹⁰⁰ , ASI ⁹⁷	IQ
Aim 3	HIV Risk Behaviors	HIV risk behaviors (HIV Risk-taking Behavior Scale ¹⁰¹⁻¹⁰³)	IQ
Aims 3, 4	Psychiatric symptoms	PTSD Checklist (PCL), ¹⁰⁴ Insomnia severity index, ¹⁰⁵	IQ
Aims 1, 3, 4	Quality of Life	Roland Morris Disability Questionnaire ¹⁰⁶ , Patient Reported Outcomes Quality of Life-HIV (PROQOL-HIV) ¹⁰⁷	IQ
Aims 1-4	Medical comorbidities	Comorbidities (obesity, cardiovascular disease, diabetes)	MR
Aims 1-4	Side effect vs benefit	Treatment Satisfaction Questionnaire for Medication (TSQM-9) ⁹¹	TQ
Aims 1-4	Urine cannabinoid	Urine GCMS for cannabinoids	

B=blood test; MR=Medical records; PR=Pharmacy records or Prescription Monitoring Program; IQ= in-person questionnaire; TQ=phone questionnaire; SSRI=selective serotonin reuptake inhibitor; TQ measures occur every week; IQ occurs at 0 and 14 weeks. B occurs at 0 at 14 weeks.

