3.B. Eligibility criteria are described in Table 4. There are no eligibility restrictions based on gender, race or ethnicity. The study population is expected to reflect the racial and ethnic composition of PLWH receiving medical cannabis in the Bronx, NY. We estimate participants' characteristics based on the characteristics of patients receiving care in the collaborating medical cannabis dispensaries and having been certified at Montefiore. Taken together, characteristics from these sites are approximately: 60% men, 15% Hispanic, 40% non-Hispanic white, 30% non-Hispanic black, 13% non-Hispanic Asian, and 2% non-Hispanic other race. Thus, we expect to enroll the following participants: 40 women, 60 men; 15 Hispanic, 85 non-Hispanic; 40 non-Hispanic white, 30 non-Hispanic black, 13 non-Hispanic Asian, 2 non-Hispanic other race (see Targeted/Planned Enrollment Table).

Justification for the exclusion of minors.

Table 9. Power calculation for Aim 1

	High THC capsules	High CBD capsules	Power
ICC=0.2	40%	15%	>0.99
ICC=0.3	40%	15%	0.99
ICC=0.4	40%	15%	0.96
ICC=0.2	40%	20%	0.97
ICC=0.3	40%	20%	0.91
ICC=0.4	40%	20%	0.84

We will not include children under the age of 18 in our study population because: a) neuropathic pain in PLWH is much more common among adults, and b) the vast majority of providers at Montefiore who certify patients for medical cannabis use provide care only for adult patients. We expect that the age range of participants will be similar to that of patients certified for medical cannabis at Montefiore. Taken together, the median age of patients seen for medical cannabis visits was 51 years, and ranges from 19 years to 94 years. This correlates well with the population of PLWH in the US, in which more than 40% are 50 years old or over¹

3.C. Data sources: *Questionnaires:* At in-person research visits, research staff will administer questionnaires using Audio Computer-Assisted Self Interview (ACASI) technology; participants will enter responses directly onto computers. During phone visits, study staff will administer questionnaires and enter answers directly into the computer. Questionnaires will focus on pain, dose of THC and CBD in medical cannabis taken, psychological symptoms, and ARV adherence (Table 3).

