Aim 3: Examine how medical cannabis use affects adverse events. *H4: Participants who use high THC (vs. high CBD) cannabis products will have more psychological symptoms, poorer ARV adherence, and less suppressed VL.* We will examine whether participants using high THC products vs high CBD products have a greater chance of adverse events, including psychological symptoms, ARV adherence, and VL. We will use mixed-effects linear regression analysis for continuous measures (VL, ARV adherence, and psychological symptoms). Each adverse event (Table 8) will be included in a separate model. We will repeat this model using alternative measures of medical cannabis (cumulative dose of THC and CBD).

Aim 4: Explore mechanisms by which medical cannabis promotes analgesia. *H5: Different doses of THC and CBD will have differing effects on inflammatory cytokines, psychological symptoms, and ultimately analgesia.*

We will use a pooled analysis of THC and CBD, using weekly questionnaires and PMP records. We will examine these relationships longitudinally in a stepwise process. First, we will conduct a mixed-effects model to examine how potential mediators lead to analgesia (reduction in BPI severity score). We will repeat analyses for possible mediators, including inflammatory cytokines and psychological symptoms. We will also determine if exposures influence changes in these variables over time, which in turn, influence change in analgesia (e.g., using time-lagged mediators and outcomes). Mediators found to be significant will be included in the final model.⁹² We will calculate the standardized total effect from the exposures to analgesia as well as the standardized mediational (i.e., indirect) effects via mediators. The mediational effect is calculated as the product of the effect from the exposures to the mediators, and the effect from the mediators to the outcome.

8) Data quality control and database management

Data management: Questionnaire, medical records, and PMP data will be de-identified and entered by study staff into a password-protected computer and database. Paper records will be stored in a locked filing cabinet that only research staff can access. Medical and PMP record data will be de-identified and entered in a secure HIPAA compliant web-based system. To protect confidentiality, we will use separate processes for ID- and name-based files and seek a certificate of confidentiality.

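### Cannabis is classed as medical or as an undefined *unregulated*, and no THC or CBD amount is listed for any non-medical product, so cumulative dose is under-counted for participants who use other sources

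*Combined protocol and SAP*

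**What the plan says.** Screening and recording name two classes of cannabis.

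- **Medical.** Section 2.C, exclusion 3, bars "medical cannabis use within 30 days prior to enrollment". Section 1.B says that a state-licensed dispensary "reports dispensed products, including milligrams of THC and CBD content and route of administration, to the NY Prescription Monitoring Program".
- **Unregulated.** Exclusion 7 bars "unregulated cannabis, opioid, cocaine, or benzodiazepine use in the past 30 days (self-report and urine drug screen". The wash-out paragraph in section 2.C uses the same term, again with urine confirmation. No section defines it.

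The weekly item in the measures table (Table 8) is "Self-reported medical and unregulated cannabis use (product, # of days used, route, dollar amount of unregulated cannabis purchased, ASI". It lists no THC or CBD amount.

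Section 1.B recognises a further class: "Medical cannabis is legal in 37 states and recreational cannabis in 18 states". The states are not named. No eligibility rule, wash-out rule or listed questionnaire item mentions recreational cannabis, and CBD bought outside the programme appears nowhere.

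On dose, section 3.C says the questionnaires cover "dose of THC and CBD in medical cannabis taken". Section 2.C makes cumulative THC and CBD over weeks 3-14 a key independent variable, and section 7.A repeats the Aim 1-3 models with it. For Aim 4, section 7.A says "We will use a pooled analysis of THC and CBD, using weekly questionnaires and PMP records".

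Urine is collected at the two in-person visits (weeks 0 and 14), and Table 8 lists urine GCMS for cannabinoids for Aims 1-4.

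**The concern.** The scientific question is whether THC and CBD content changes the effect on pain, so the plan needs to know how much of each a participant took. A licensed non-medical product is regulated in the ordinary sense of the word, yet it is not dispensed under the medical programme. Retail CBD is in the same position. Staff and participants, some of whom answer online, have to decide for themselves whether such use counts as *unregulated*, and they may decide differently.

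Two things are at stake. First, the dose variables used in every aim omit THC or CBD from such sources. Second, if high-CBD users take outside THC, the two product groups become more alike. Participants are not randomised, so supplementing may also differ by group, which could bias the comparison as well as dilute it. Amounts not collected week by week cannot be filled in at analysis.

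**Working it through.** **1. Where each class of product would be recorded**

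| Place in the plan | Programme product | Unlicensed cannabis | Licensed non-medical cannabis, or CBD from outside the programme |
|---|---|---|---|
| Exclusion 3 | covered | not covered | not covered |
| Exclusion 7 and wash-out (self-report) | not covered | covered | depends on the meaning of *unregulated* |
| Weekly item, Table 8 | product, days, route | product, days, route, dollars | depends on the meaning of *unregulated* |
| PMP, as described in 1.B | milligrams of THC and CBD | none | none |
| Dose questions, 3.C | asked | not stated | not stated |
| Urine, weeks 0 and 14 | independent of source | independent of source | independent of source; analytes not listed, so CBD detection unknown |

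**2. Both readings of the undefined term**

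- *Narrow (unlicensed only).* The last column is neither excluded by self-report nor asked about each week.
- *Broad (anything outside the programme).* Use may be reported, but the listed fields are product, days, route and dollars. None is an amount of THC or CBD.

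**3. Consequence for cumulative dose**

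True dose = programme dose + other dose. The listed inputs give an amount for the first term only, so the shortfall equals the other dose under either reading. Of the two urine samples, only week 14 falls in the weeks 3-14 window. A positive result there is expected, because section 3.C uses urine to confirm that participants are taking medical cannabis.

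**4. Possible dilution of the product contrast (illustration)**

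Inputs from section 3.A and Table 9: 42 per arm, 40% against 20%, two-sided 5%, ICC 0.4, stated power 0.84. I take 14 weekly responses per person.

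Effective n per arm = 42 × 14 / (1 + 13 × 0.4) = 588 / 6.2 = 94.8.

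Power = Φ(|logit p1 − logit p2| / SE − 1.96), with SE² = 1/(94.8·p1·(1−p1)) + 1/(94.8·p2·(1−p2)).

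The plan's figure: 0.981 / 0.331 = 2.96, and Φ(1.00) = 0.841, which matches 0.84. With ICC 0.3 (effective n 588/4.9 = 120.0) and ICC 0.2 (588/3.6 = 163.3), the formula gives 0.91 and 0.97, also as in Table 9.

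Now let a share f of the high-CBD group take outside THC and respond at 40%, so p2 = 0.20 + 0.20f.

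| f | p2 | Difference (points) | Log-odds difference | SE | Power |
|---|---|---|---|---|---|
| 0 | 0.20 | 20 | 0.981 | 0.331 | 0.841 |
| 10% | 0.22 | 18 | 0.860 | 0.325 | 0.755 |
| 20% | 0.24 | 16 | 0.747 | 0.319 | 0.649 |
| 30% | 0.26 | 14 | 0.641 | 0.314 | 0.531 |

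A two-proportion formula on the same effective n gives 0.858, 0.769, 0.658 and 0.536. The documents give no value for f.

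**The case against.** *Unregulated* is used throughout as the counterpart of *medical*, and a natural working meaning is anything obtained outside the programme. Table 8 only summarises a questionnaire that is not in the documents. A participant could report licensed non-medical cannabis under it, and the ASI, whose items are not shown, might capture it too. This stands as far as it goes: the firm finding is an undefined term, not proof that such use is never asked about. It does not repair the dose variable, since no amount is listed even on the broad reading.

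A reader might infer that outside cannabis goes wholly unseen and that current users can simply enter. The documents do not support that. Exclusion 7 and the wash-out require a urine screen as well as self-report, and urine results do not depend on where a product was bought.

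A reader might also infer that the primary comparison is misclassified. It is not: group is the initial product dispensed, analysed by intention to treat, and co-use does not change membership. Cumulative dose is the secondary independent variable.

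Only section 3.C limits dose to medical cannabis; the wording in section 2.C and under Aim 4 is open. That is fair, but open wording supplies no amounts.

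Finally, the shares in the power table are invented, every co-user is assumed to move to the full 40%, and dilution would lower power even if co-use were recorded. All of that stands.

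**Conclusion.** The point holds as a gap in exposure measurement. *Unregulated* is undefined, so licensed non-medical cannabis and CBD from outside the programme have no clear place in exclusion 7, the wash-out rule or the weekly item. On either reading, the plan lists no THC or CBD amount for any non-medical product, and cumulative dose is under-counted for participants who use one. This affects the dose-based repeats of Aims 1-3 and the whole of Aim 4. Urine offers a partial, source-blind check at two time points.

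The practical importance rests on an assumption. The documents do not say that recreational cannabis is sold legally in New York or that retail CBD is available to participants. A reader might take the section 1.B sentence on recreational legalisation as saying so, but it names no state. How common co-use would be is unknown, so the fall from 84% to about 76%, 65% or 53% shows direction and possible size and is not an estimate. The change is worth making because it is cheap and the missing amounts cannot be recovered later.

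**What to change.** - **Weekly questionnaire.** Ask about any cannabis or CBD product not dispensed under the state medical programme, licensed or not: source, product, labelled THC and CBD where known, and days used.
- **Dose variable.** State in section 7.A that labelled amounts from these products enter cumulative THC and CBD dose, and flag use of unknown content.
- **Reporting.** Tabulate such use by product group. Add a sensitivity analysis that accounts for it, labelled as conditioning on post-baseline behaviour. Dropping co-users should not replace the main comparison, since in a non-randomised cohort that may add selection bias.
- **Urine.** Name the GCMS analytes and say how the results inform the product-group and dose analyses.
- **Definition.** Give *unregulated* one meaning in exclusion 7, Table 4 and the wash-out rule. Whether CBD from outside the programme is an exclusion is a new eligibility question and should be left to the investigators.

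The cost is a protocol amendment and one or two items in a 5-7 minute questionnaire, so slightly longer weekly calls. For participants already followed, amounts may not be recoverable, but the definition and the analysis rule can still be fixed before analysis.

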In-person visits: Participant's 2 in-person visits will occur in private rooms at the Montefiore/Einstein ICTR Clinical Research Center. At the baseline visit, study staff will describe the study and obtain written informed consent. Tracking forms as well as agreements to release medical, pharmacy, and PMP records will be completed. Participants will receive a refillable debit card for compensation. At all in-person visits, we will administer questionnaires, and collect blood and urine samples. Participants will receive \$27.50 for each in-person visit.

Phone or web visits will occur weekly over 14 weeks and include brief (5-7 minute) questionnaires administered by study staff over the phone or completed on-line. A total of 15 visits will occur, the first at baseline, when participants can be trained on how to complete it, and then one at the end of each week of the follow-up period. Participants will receive \$3 on debit cards after completing each phone or web-based questionnaire.

Blood draws will occur at week 0 and 14 in-person visits. They will measure VL, CD4 count, pro- and anti-inflammatory cytokines. Participants will be compensated an additional \$15 for each visit in which there is a blood draw.

Main independent variable will be the soft gel capsule product dispensed at Vireo, including a 1) high THC capsule, or 2) high CBD capsule. Other key independent variables will be cumulative THC and CBD taken (weeks 3-14, continuous measures).

Main outcome variables: Our primary outcome is pain severity, measured via the BPI severity scale (ordinal variable), as recommended by a committee of international pain experts.⁹² It is an 11-point (0-10) numerical rating scale of pain intensity, where 0 is 'No pain' and 10 is 'Pain as

bad as you can imagine'. Participants will complete the BPI severity scale in each phone visit (baseline and at each weekly visit).

Pro- (TNF α , IL-1 β , IL-6) and *anti-* (IL-4, IL-10) *inflammatory cytokines (secondary outcomes;* 0, 14 week *blood draws*) will be measured with Luminex assay and reported as picograms per mm 3 (continuous measure).

Adverse events (secondary outcomes) will be ARV adherence (AIDS Clinical Trial Group [ACTG] Adherence Interview,^{93,108} Adherence Visual Analog Scale [VAS; weekly]),⁹⁴ VL suppression (blood draws at 0, 14 weeks; copies/mL); and psychological symptoms—depression (CES-D; 0 and 14 weeks),⁹⁵ anxiety (GAD-7; 0 and 14 weeks),^{96,94,97,109}

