Medical record data will be extracted 6 months prior to enrollment through 14 weeks after enrollment, including medical cannabis certification forms, prescriptions, and notes regarding pain treatment (nerve blocks, physical therapy, occupational therapy).

Pharmacy and PMP records will be extracted for medications dispensed 6 months prior to enrollment to 14 weeks after enrollment. Data will include ARVs, controlled substances (e.g., dispensed medical cannabis products, THC and CBD content in milligrams, doses dispensed) and pain medications (i.e., anticonvulsant, selective serotonin reuptake inhibitor, topical lidocaine).

Blood draws: Approximately 15 ml of blood will be drawn to assess VL, CD4 count, pro-inflammatory and anti-inflammatory cytokines. *VL and CD4 count* will be processed through Montefiore's central lab. VL will be quantified using the Abbott RealTime HIV-1 Viral Load assay (Abbott Park, Illinois), and CD4 count will be measured by the BD Multitest (BD Biosciences, San Jose). *Pro- (TNF α , IL-6) and anti- (IL-4, IL-10) inflammatory cytokines* will be analyzed using the Olink cytokine assay (Thermo Fisher Scientific, Waltham, MA) at Mount Sinai's Human Immune Monitoring Center.

Urine samples: We will check urine drug screens to confirm that patients are taking medical cannabis and to confirm that they abstain from opioid use during the course of the study.

4) Recruitment

4.A. Recruitment will occur from Montefiore's Medical Cannabis Program in which 25 patients are certified per month. Of those, approximately 6 are PLWH. In June 2020, [name] expanded the program to include Montefiore's HIV clinic, where 2500 PLWH receive care. With this expansion, at least 20 PLWH per month are certified for medical cannabis, and an overwhelming majority have pain. We will also leverage the clinical core of the ERC-CFAR to identify and recruit PLWH with neuropathic pain. Through these targeted clinical activities, we anticipate that enrolling 100 PLWH over 36 months (3-4/month) will be feasible.

Participant tracking: To facilitate tracking participants over 14-weeks, we will record: 1) participants' address and phone numbers; 2) contact information of family or friends; and 3) locations where participants work. This method allowed for 85% retention over 6 months of follow up in previous research studies.⁸⁵⁻⁸⁷

4.B. Participant retention

We will use previously established methods by my mentors to maximize retention in clinical trials.

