Subject tracking and appointment reminders. At all visits, we will record: 1) participants' address and phone numbers; 2) contact information of family or friends; and 3) locations where participants work. Locator forms will be updated at all visits.

Screening process. After obtaining oral informed consent, a standardized screening process will occur by phone or in-person. Eligible participants will be scheduled for a baseline visit and written informed consent will be obtained.

Loss to follow up. We conservatively estimate a 15% loss to follow up. [name] has achieved 85% retention over 6-month follow-up in difficult to reach populations.

5) Informed Consent

Informed consent will be obtained from participants by the research assistant. Potential participants will first complete an oral consent prior to completing a screening questionnaire by phone. Included in this consent is verbal consent to reviewing the PMP. If they are eligible for the study, they will be scheduled for an enrollment visit, as which time a written informed consent will be completed.

Participant Compensation. Participant reimbursement will be given to compensate for time and inconvenience. Participants will be compensated \$27.50 for each in-person visit (of which there will be 2) and an additional \$15 for each visit in which there is sample collection (blood draw, urine collection; of which there will be 2). Participants will complete 15 total weekly phone visits. They will be compensated \$3 for each completed phone visit (total \$45/participant for phone-based surveys). Thus, if participants remain in the study for the full 14-week study period, they will receive a total compensation of \$130.

6) Risk Benefit

6.A. Potential Risks. We identified four potential risks to participants: (1) breach of confidentiality regarding HIV or certification for medical cannabis, (2) Discomfort with participation, (3) fear that refusal to participate will affect care or services, and (4) inconvenience and discomfort associated with phlebotomy.

1. *Confidentiality issues:* We will collect personal information from participants to follow-up if they are interested in participating in subsequent parts of the study. We have outlined our procedures to address maintaining confidentiality below

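### Cytokines, viral load, CES-D and GAD-7 have one post-baseline measurement, at week 14, and no early-exit assessment, so about 15 of 100 participants would have no follow-up value

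*Combined protocol and SAP*

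**What the plan says.** All references are to the combined protocol and SAP.

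- **Schedule.** Section 2.C (blood draws) states: "Blood draws will occur at week 0 and 14 in-person visits". The footnote to the measures table (cited as Table 8) gives the rule for every source: "TQ measures occur every week; IQ occurs at 0 and 14 weeks. B occurs at 0 at 14 weeks". The outcome paragraph of 2.C repeats it by instrument: "VL suppression (blood draws at 0, 14 weeks; copies/mL", "depression (CES-D; 0 and 14 weeks" and "anxiety (GAD-7; 0 and 14 weeks". The Aim 2 analysis in 7.A uses the same two times for cytokines.
- **Weekly data.** The weekly phone or web contacts carry BPI severity, TSQM-9 and cannabis use. Section 2.C adds a weekly adherence visual analogue scale (VAS), although the measures table codes it as an in-person item.
- **Loss.** Section 4.B says: "We conservatively estimate a 15% loss to follow up". Section 3.A applies 15% to each group and arrives at 42 per group.
- **Records.** Section 3.C says: "Medical record data will be extracted 6 months prior to enrollment through 14 weeks after enrollment". The items it then names are certification forms, prescriptions and notes on pain treatment.
- **Missing data.** Section 7.A plans multiple imputation by Markov chain Monte Carlo and a comparison with the data set without the missing values. It plans no other missing-data sensitivity analysis. Reasons for leaving are not among the listed data.

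**The concern.** A participant who leaves in, say, week 6 has already given weekly pain scores, so the primary outcome keeps part of that person's follow-up. For cytokines, VL, depression and anxiety the same person gives a baseline value and nothing else.

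This matters most for H4, which predicts more psychological symptoms and less suppressed VL on high-THC products. If some people leave because their mood or anxiety worsened, the values that would show it are the ones not collected. Every observed week-14 value comes from someone who stayed, and both planned analyses depend on those values. For the cytokine hypotheses (H2 and H3) the same data are missing, but an argument based on harm does not carry over to them.

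**Working it through.** **1. The plan's own figure.** Inputs from 3.A: 100 participants, about 50 per group, 15% loss in each.

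- Remaining per group: 50 × (1 − 0.15) = 42.5. The plan's 42 is this rounded down, so it reproduces.
- Leaving: 0.15 × 100 = 15 in total, or 7.5 per group.

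**2. What those 15 would contribute after baseline**

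| Outcome | Post-baseline times | Value from a leaver |
|---|---|---|
| Cytokines | week 14 | none |
| VL | week 14 | none from study blood |
| CES-D, GAD-7 | week 14 | none |
| ARV adherence | weekly VAS (per 2.C), pharmacy fills | yes, partly |
| BPI severity | weekly | yes, up to exit |

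**3. What the planned analyses can see.** Imputation can condition on a leaver's baseline and weekly data. It then assumes that, given those data, the unseen week-14 value follows the same relation as in people who stayed. The complete-case comparison also uses only people who stayed. Agreement between the two would therefore not rule out exit caused by harm.

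**4. Possible size.** On a scale where higher is worse, let L be the proportion leaving and D the amount, in SD, by which leavers are truly worse than the value imputed for them. The harm missed in the high-THC minus high-CBD contrast is

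shift = L(THC) × D(THC) − L(CBD) × D(CBD).

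The documents give L = 0.15 in each group. They give no D, so 0.5 to 1.0 SD is an assumption.

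- Same D in both groups: 0.15 × D − 0.15 × D = 0.
- Only high-THC leavers worse: 0.15 × 0.5 = 0.075 SD, to 0.15 × 1.0 = 0.15 SD. Against the d = 0.5 target in 3.A this is 0.075/0.5 = 15% to 0.15/0.5 = 30%.
- Only high-CBD leavers worse: the same sizes with the opposite sign.

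Unequal loss departs from the plan's assumption. With the same total of 15 and the same D in both groups:

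- 20% against 10%: (0.20 − 0.10) × D = 0.05 to 0.10 SD.
- 25% against 5%: (0.25 − 0.05) × D = 0.10 to 0.20 SD.

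**The case against.** A reader might infer more than the documents support.

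- **That everyone who stops cannabis is lost.** Stopping the product is not leaving the study. Section 7.A uses intention-to-treat and a separate per-protocol set based on at least 3 months of use, which implies that people with shorter use stay in follow-up. This stands: the gap concerns only those who leave follow-up.
- **That the safety comparison is biased toward no harm.** Nothing links the 15% to harm; it is backed by retention experience in other studies, and 3.A applies it equally to both groups. With equal loss and equal harm the shift is 0. This stands: the direction is conditional.
- **That imputation rests only on people who stayed.** Leavers' own BPI, TSQM-9 and VAS values before exit can inform it, although 7.A does not name the imputation variables. This reduces the concern but does not remove the missing-at-random assumption.
- **That all of H4 is uncovered.** Adherence has post-baseline data. Section 3.C also mentions psychological symptoms in questionnaires, but it describes in-person and phone questionnaires together, and 2.C fixes CES-D and GAD-7 at weeks 0 and 14.
- **That charts exclude VL.** The list in 3.C is introduced as a set of examples, so omission is weak evidence. The measures table does give blood as the only source for VL.

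It is also fair to say that a remedy cannot reach people who have disappeared, that weekly forms may be completed online without staff contact, and that an early value is not the week-14 change the plan models. These limit the benefit.

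**Conclusion.** The gap in data collection is real. At the plan's own 15% loss, about 15 of 100 participants would have no post-baseline cytokine, VL, CES-D or GAD-7 value. The text available for review, which is not the whole document, describes no early-exit assessment.

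Bias in H4 follows only if leaving is related to harm, beyond what the weekly data explain, and the pattern differs between products. Its size is unknown. With 15% loss in each group and an assumed gap of 0.5 to 1.0 SD, it runs from 0 to about 0.15 SD, and the documents do not settle the direction. The primary outcome is measured weekly and does not have this gap. This is a worthwhile, inexpensive improvement to secondary outcomes; it does not show that the safety comparison is already biased.

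**What to change.** - When a participant tells staff that they are withdrawing or cannot attend week 14, offer the planned week-14 assessment at that time: CES-D, GAD-7 and the ACTG adherence interview, by telephone if needed, and the blood draw if they agree.
- Record the reason for leaving, the actual week and the mode of each assessment.
- Use these values in the mixed models at their actual time and as predictors in the imputation. Add a sensitivity analysis that excludes early or telephone values.
- Add clinical VL results through week 14 to the existing chart extraction, for everyone who has not revoked the record release.

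**Cost.** Protocol wording, a short exit form, a VL field in the extraction and one sensitivity analysis. The assessment is moved, not added: its payment of $27.50 + $15 = $42.50 is already budgeted.

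**Downsides.** Some values will be early, and some will be taken by telephone instead of by computer self-entry (ACASI), which may change answers to sensitive items in the very group of interest. Participants who cannot be contacted will still lack questionnaire and cytokine data, and the documents give no basis for estimating how many of the 15 would take up the offer.
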